8.3.5. Key Elements of Analysis Plan

8.3.5.1. Efficacy Analyses

8.3.5.1.1. Primary Analysis

The primary objective of the statistical analysis will be to test the null hypothesis in the ITT population that there is no difference between retosiban and atosiban in time to delivery versus the alternative hypothesis that there is a difference.

The primary analysis of time to delivery will utilize a finite mixture model [McLachlan, 2000] with 2 components, 1 for those women that delivery imminently and the other for the women delivering at term. The exact weight of each component will be determined by the observations from the component and model concomitant variables including treatment and GA at randomization. Within each component, the expected time to delivery will be modeled as a function of treatment as fixed effect and GA at randomization and established progesterone use (yes or no) as a covariate. The model parameters will be estimated using expectation-maximization algorithm. Point estimates, associated 95% CIs, and p-values for the overall average difference in time to delivery between retosiban and atosiban will be derived using the weighted average of model parameter estimates and variance from each subpopulation of mixture model. Details of mathematical model and analysis will be included in the RAP.

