2.4. Statistical Hypotheses

The primary endpoint is prolongation of pregnancy as measured by time to delivery (days). The following are the null (H_0) and alternative (H_1) hypotheses for the primary endpoint in this study:

- H_0 : The prolongation of pregnancy as measured by time to delivery is equal between the women randomized to retosiban versus atosiban
- H_1 : The prolongation of pregnancy as measured by time to delivery is unequal between the women randomized to retosiban versus atosiban

The primary objective of the statistical analysis will be to test the null hypothesis in intent-to-treat (ITT) Population that there is no difference between retosiban and atosiban and the alternative hypothesis that there is a difference for the primary endpoint. The hypotheses will be tested at 5% level in a 2-sided test.

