
above and some patients are pre-assigned to each component to stabilize the model, i.e. the first component includes those deliveries within 1 week of GA at randomization and the second component includes the patients who deliver after 38 weeks of GA.
 
The model parameters can then be estimated using PROC FMM from SAS 9.4 by maximizing the likelihood. Point estimate, associated 95% confidence intervals and p-values for the overall average difference between Retosiban and Atosiban is then derived using weighted average of model parameter estimates and variance from each sub-population of mixture model.
 
 • Additionally, treatment by GA at randomization interaction and treatment by progesterone use interaction will also be investigated. • Terms fitted in the FMM model will include: 
 
 Fixed Categorical:	TRT, EP and their interaction term (TRT*EP). Interaction will be included only if the interaction is statistically significant (at 0.05 level of significance).	
 
 Fixed Continuous Covariates:	GA and interaction term (TRT*GA). Interaction will be included only if both interaction are statistically significant (at 0.05 level of significance).	
 
 Repeated:	None	
 
 		Fixed Categorical:	TRT, EP and their interaction term (TRT*EP). Interaction will be included only if the interaction is statistically significant (at 0.05 level of significance).	Fixed Continuous Covariates:	GA and interaction term (TRT*GA). Interaction will be included only if both interaction are statistically significant (at 0.05 level of significance).	Repeated:	None
Fixed Categorical:	TRT, EP and their interaction term (TRT*EP). Interaction will be included only if the interaction is statistically significant (at 0.05 level of significance).						
Fixed Continuous Covariates:	GA and interaction term (TRT*GA). Interaction will be included only if both interaction are statistically significant (at 0.05 level of significance).						
Repeated:	None						
SAS Code							
<pre>proc fmm data=xxx TECHNIQUE=xxx. partial=xxx ; class TRT EP; model T2D = TRT EP GA TRT*GA TRT*EP/ k=2; probmodel TRT EP GA TRT*GA TRT*EP; run;</pre>							
Model Checking & Diagnostics							

 • Refer to Appendix 9: Model Checking and Diagnostics for Statistical Analyses. 							
Model Results Presentation							

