	
 • For the endpoints of neonatal composite outcome, proportion of births prior to $37^{0/7}$ weeks' gestation, and proportion of births at term ($37^{0/7}$ to $41^{6/7}$ weeks' gestation), a logistic regression model will be used for comparing retosiban with atosiban, with GA at randomization and established progesterone use (yes or no) as covariates. The model will use a logit link function to estimate the log odds of percentage of preterm birth. The model will include terms for treatment group, established progesterone use, and GA at randomization. Additionally, interactions between GA at randomization and treatment and established progesterone use and treatment will also be investigated. • Length of hospital stay will be log-transformed (at base 10) prior to analysis. Log-transformed length of hospital stay will be analyzed using an analysis of covariance adjusting for the covariate of GA at randomization and established progesterone use (yes or no). Additionally, interactions between GA at randomization and treatment and established progesterone use and treatment will also be investigated. Wilcoxon rank sum test will also be performed to compare the two treatments if length of hospital stay is not log normal. • Terms fitted in the model will include: Fixed Categorical: TRT, EP and their interaction term (TRT*EP). Interaction will

Key Secondary Efficacy Statistical Analysis	
Fixed Continuous Covariates:	be included only if the interaction is statistically significant (at 0.1 level of significance). GA and interaction term (TRT*GA). Interaction will be included only if the interaction is statistically significant (at 0.1 level of significance).
Repeated:	None
SAS Code	

 Analysis of Covariance: <pre>ods output lsmeans=means diff=diffs tests3=tests; proc mixed data=xxx; class EP TRT; model log_LoS= TRT EP GA TRT*EP TRT*GA/ddfm=kr s; lsmeans TRT /pdiff cl alpha=0.05; run;</pre> Wilcoxon rand sum test: <pre>proc npar1way data=xxx Wilcoxon; class TRT; var log_LoS; ods output wilcoxontest=wtest; run;</pre> 	
Model Checking & Diagnostics	

 Refer to Appendix 9: Model Checking and Diagnostics for Statistical Analyses. 	
Model Results Presentation	

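### Treatment interactions enter the primary and key secondary models by significance test, the printed code always fits them, and the treatment contrast is then undefined

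*SAP*

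**What the plan says.** **Primary model, SAP 7.1.2.** Time to delivery is fitted with a two-component normal mixture. The equations contain treatment, GA and established progesterone use (EP) as main effects, in both the component means and the mixing probabilities. The list of fitted terms then adds interactions conditionally. For TRT*EP: "Interaction will be included only if the interaction is statistically significant (at 0.05 level of significance". For TRT*GA: "Interaction will be included only if both interaction are statistically significant (at 0.05 level of significance". The SAP does not say what the word both refers to.

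The sample code has no condition: "model T2D = TRT EP GA TRT*GA TRT*EP/ k=2", with the same terms repeated in PROBMODEL. The overall average difference "is then derived using weighted average of model parameter estimates and variance from each sub-population of mixture model"; no GA or EP value, or averaging rule, is given.

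**Key secondary models, SAP 8.1.2.** Each interaction is tested at a looser level: "Interaction will be included only if the interaction is statistically significant (at 0.1 level of significance". The length-of-stay code again fits both terms outright, "model log_LoS= TRT EP GA TRT*EP TRT*GA/ddfm=kr s", and takes the treatment difference from an LSMEANS statement.

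**Elsewhere.**
- Protocol 8.3.5.1.1 has no interaction: "Within each component, the expected time to delivery will be modeled as a function of treatment as fixed effect and GA at randomization", together with EP.
- Protocol 8.3.5.1.2 plans to look at the interactions but gives no rule for keeping them.
- The code in SAP 11.7.2 (composite) and 11.7.4 (length of stay) contains treatment, GA and EP only.
- SAP section 9, which lists departures from the protocol, does not mention the inclusion rule.
- SAP 2.4 keeps the nominal level: "The hypotheses will be tested at 5% level in a 2-sided test".

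**The concern.** Two problems meet here.

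First, the model that yields the reported treatment difference depends on a preliminary test in the same data. When an interaction enters, the difference may change meaning. With LSMEANS it becomes an average that gives progesterone users and non-users equal weight, whatever their shares. With a raw coefficient it becomes the effect at GA = 0 weeks in the reference EP group, although eligibility runs from 24 0/7 to 33 6/7 weeks. Either contrast is correlated with the interaction estimate that triggered selection, so the nominal 5% level need not hold.

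Second, the SAP carries three incompatible models: main effects (equations, Appendix 7), conditional interactions (text) and unconditional interactions (code). Two programmers could each follow the SAP and report different estimates, intervals and p-values.

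**Working it through.** **1. The plan's own figure.** Protocol 8.2.1 gives 86% power for 9.5 days with 150 evaluable women per arm, a futility look at about 130, and simulated type I error of 2.4%. No SD is stated, so power cannot be rebuilt in days (a fixed two-sample z-test would need an SD of about 27.1 days). It can be rebuilt from the stopping probabilities:
- information fraction 130/300 = 0.433, square root 0.658;
- 74% futility under the null gives an interim bound of z = 0.643;
- 7% futility under the alternative gives an interim mean of 0.643 + 1.476 = 2.119, and a final drift of 2.119/0.658 = 3.22;
- with final rejection at |z| > 1.96, power is 86.1% and type I error 2.2%.

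The design figures are coherent. Whether the 2.4% covered the interaction step cannot be checked, because the simulation report is a separate document.

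**2. How often a term is kept under the null**, treating the two tests as independent:
- primary rule as written: TRT*EP enters with probability 0.05; TRT*GA needs both to pass, 0.05 x 0.05 = 0.25%. At least one is kept in about 5%.
- key secondary rule: 1 - 0.90^2 = 19%.

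**3. Why the contrast matters.** Let p be the share of progesterone users, m the mean GA, and b_EP and b_GA the interaction coefficients.
- LS-means contrast = standardised contrast + (0.5 - p) x b_EP.
- Raw TRT coefficient = standardised contrast - p x b_EP - m x b_GA.

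The standardised contrast, averaged over the trial's own GA and EP mix, has no such added term. The other two carry a multiple of the estimate on which selection was based.

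**4. Null simulation.** Inputs: GA strata 1:2:4:8 (Protocol 8.2.1), 1:1 allocation, N = 97 (SAP synopsis). EP prevalence is not in the documents and is assumed at 10, 20 and 30%. ANCOVA is the planned method for log length of stay but only a stand-in for the primary mixture. There were about 40,000 runs per row and prevalence, so the Monte Carlo standard error at 5% is about 0.1 point. Rejection rates are listed in prevalence order:

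| Rule, N=97 | Term kept | Main effects | LS-means | TRT coefficient | Standardised |
|---|---|---|---|---|---|
| Primary, as written | 4.8-5.0% | 5.0-5.2% | 7.3 / 6.0 / 5.6% | 5.7 / 5.7 / 6.0% | 5.2 / 5.0 / 5.0% |
| Key secondary, 0.1 | 18.9-19.0% | 5.0-5.1% | 7.9 / 6.7 / 5.9% | 9.9 / 10.5 / 10.6% | 5.1 / 5.2 / 5.1% |

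- TRT*GA entered in 0.3% of null trials under the primary rule, so the TRT*EP line does most of the work.
- At N = 300 under the 0.1 rule, LS-means gave 7.8 / 7.0 / 6.1%, so a larger trial does not remove the effect.
- A further set of null runs (N = 97, 10-20% EP) gave 6.6-8.6% for LS-means under the 0.1 rule; 5.5-7.1% (LS-means) and 5.3-6.3% (coefficient) under the primary rule; and 4.5-5.9% standardised.
- If outcome variance depends on GA, retention under the 0.1 rule rises to about 26%.

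**5. Logistic key secondary endpoints, 0.1 rule.** At N = 97 (6,000 runs) the raw coefficient rejects in 9.5 / 9.6 / 10.8%, against 4.8-5.1% for main effects. An equal-weight contrast gives 5.0 / 5.5 / 5.5%. Runs with separation were dropped, 34% of them at 10% EP.

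**6. The code as printed, with no selection.** Fitting both terms always does not inflate error, but it costs precision. With equal residual variance the LS-means SE ratio to main effects is 1/sqrt(4p(1-p)): 1.67, 1.25 and 1.09 at p = 0.1, 0.2 and 0.3. For the raw coefficient, taking GA as uniform within the planned strata, m = 30.5 and SD = 2.6 weeks. The ratio is about sqrt(1 + (30.5/2.6)^2), or roughly 12.

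**The case against.** The rule and its thresholds are written down in advance, and the SAP synopsis fixes analysis decisions before database freeze. A reader might infer that the whole target of estimation is left open until unblinding. That goes too far: what is missing is the definition of the contrast.

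A reader might also infer that the primary test runs at about 14-17%, with an interaction kept in 14-16% of trials. The documents do not support this. Such figures arise only if the requirement that both interactions be significant is ignored, or if the 0.1 rule is applied, and only when the treatment coefficient at GA = 0 is read in bimodal data. In such data a constant-variance TRT*GA test itself rejects in 11-12% of null trials at nominal 5%. That is misfit of the ANCOVA stand-in and shows nothing about the mixture model. SAP 7.1.2 also reports an overall average difference, not a coefficient, and its code has no LSMEANS statement.

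Finally, inflation is not inevitable. Averaging over the trial population is a natural reading of an overall average difference, and it holds about 5%. All of this stands. It limits the size of the problem, but it does not remove the data-driven rule, the undefined contrast, or the conflict among text, code and Appendix 7.

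**Conclusion.** The point holds in moderate form. The inclusion rule is data-driven in the primary and key secondary models, the printed code contradicts it, and the protocol's primary model, the SAP equations and Appendix 7 contradict both.

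Size: about 6-9% type I error for length of stay under the 0.1 rule with the printed LSMEANS, and about 10% for the logistic endpoints if a raw coefficient is read. The primary analysis is affected only modestly, about 5.5-7% if an LS-means-type contrast or raw coefficient is used, mainly through the TRT*EP rule.

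These figures rest on assumed progesterone use of 10-30%, on ANCOVA in place of the mixture, and on simulated outcome distributions that the documents do not supply.

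It should be fixed, but it does not undermine the trial. Enrolment stopped at 97 of about 330, and SAP 5.2 drops multiplicity adjustment. Even so, SAP 2.4 keeps a 5% test, SAP 8.1.2 keeps sequential 5% testing, and SAP 7.1.2 and 8.1.2 still call for confidence intervals and p-values.

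**What to change.** Before database freeze:
- name the main-effects model (TRT, GA, EP) as the only model for the reported treatment difference in the primary and key secondary analyses;
- delete TRT*GA and TRT*EP from the MODEL and PROBMODEL statements in SAP 7.1.2 and from the MODEL statement in SAP 8.1.2;
- report the interaction tests separately, labelled exploratory, with no effect on the reported difference;
- state how the primary overall average difference is computed, standardised over the trial's GA and EP distribution;
- make the SAP 7.1.2 equations, text and code, the SAP 8.1.2 text and code, and the code in 11.7.2 and 11.7.4 agree.

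In the simulations main effects alone hold 5.0-5.2% (ANCOVA) and 4.8-5.1% (logistic) at N = 97. The cost is some SAP wording, two terms removed from three statements, and a short definition of the contrast. No new data are needed.

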8. SECONDARY AND EXPLORATORY ANALYSES

8.1. Secondary Efficacy Analyses

8.1.1. Overview of Planned Efficacy Analyses

The secondary efficacy analyses will be based on the Maternal and Neonatal ITT Populations.

Table 4 provides an overview of the planned efficacy analyses with further details of data displays presented in Appendix 11: List of Data Displays.

Table 4 Overview of Planned Efficacy Analyses

	Stats Analysis			Summary		Individual	
	T	F	L	T	F	F	L
Key Secondary Endpoints							
Proportion of births prior to 37 ^{0/7} weeks' gestation – ascertain the GA at delivery based on a records review	Y			Y			
Proportion of births at term (37 ^{0/7} to 41 ^{6/7} weeks' gestation) – ascertain the GA at delivery based on a records review	Y			Y			
Length of neonatal hospital stay – duration (in days) of neonatal hospital admission from the medical records	Y			Y			Y
Neonatal composite endpoint	Y			Y			Y
Other Secondary Endpoints							
Individual neonatal composite endpoint				Y			Y
Neonatal composite endpoint without RDS	Y			Y			Y
Neonatal composite endpoint without RDS and mortality	Y			Y			Y
Neonatal admission to a specialized				Y			Y

	Stats Analysis			Summary		Individual	
	T	F	L	T	F	F	L
care unit and length of stay							
Newborn hospital readmission and length of stay				Y			Y
Proportion of births prior to 28 ^{0/7} weeks' gestation	Y			Y			
Proportion of births prior to 32 ^{0/7} weeks' gestation	Y			Y			
Proportion of births prior to 35 ^{0/7} weeks' gestation	Y			Y			
Proportion of births ≤7 days of IP administration	Y			Y			
Proportion of births ≤48 hours of IP administration	Y			Y			
Proportion of births ≤24 hours of IP administration	Y			Y			

NOTES :

- T = Table, F = Figure, L = Listing, Y = Yes display generated.
- Stats Analysis = Represents TFL related to any formal statistical analyses (i.e. modelling) conducted.
- Summary = Represents TF related to any summaries (i.e. descriptive statistics) of the observed raw data.
- Individual = Represents FL related to any displays of individual subject observed raw data.

1. Will be presented in the integrated analysis.

Following review of the data, additional analyses maybe conducted to further support the evaluation and interpretation of the data.

8.1.2. Planned Key Secondary Efficacy Statistical Analyses

Key Secondary Efficacy Statistical Analysis	
Endpoint	
	
 • Proportion of births prior to $37^{0/7}$ weeks' gestation • Proportion of births at term ($\geq 37^{0/7}$ weeks' gestation) • Length of neonatal hospital stay • Proportion of neonates with any diagnosis from the neonatal morbidity and mortality composite determined up to 28 days after EDD (of $40^{0/7}$ weeks) (details for each composite are provided in Section 11.5.4.)

To preserve the overall type I error rate, the key secondary analysis will be performed if and only if the null hypothesis of the primary endpoint is rejected. In addition, a sequential testing method will be used to adjust for multiplicity of the key secondary endpoints such that the type I error rate will be maintained at 5%. The sequential testing examines the hypothesis testing in a pre-specified order, i.e., the testing of the second secondary endpoint will be performed only if the first secondary endpoint is significant at 5%, and testing of the third secondary endpoint will be performed only if the first and second endpoints are significant at 5%.
 
Order of sequential testing is
 
 1) Length of neonatal hospital stay 2) Proportion of births prior to $37^{0/7}$ weeks' gestation and Proportion of births at term 3) Neonate composite outcome 	
Model Specification	
	
 • For the endpoints of neonatal composite outcome, proportion of births prior to $37^{0/7}$ weeks' gestation, and proportion of births at term ($37^{0/7}$ to $41^{6/7}$ weeks' gestation), a logistic regression model will be used for comparing retosiban with atosiban, with GA at randomization and established progesterone use (yes or no) as covariates. The model will use a logit link function to estimate the log odds of percentage of preterm birth. The model will include terms for treatment group, established progesterone use, and GA at randomization. Additionally, interactions between GA at randomization and treatment and established progesterone use and treatment will also be investigated. • Length of hospital stay will be log-transformed (at base 10) prior to analysis. Log-transformed length of hospital stay will be analyzed using an analysis of covariance adjusting for the covariate of GA at randomization and established progesterone use (yes or no). Additionally, interactions between GA at randomization and treatment and established progesterone use and treatment will also be investigated. Wilcoxon rank sum test will also be performed to compare the two treatments if length of hospital stay is not log normal. • Terms fitted in the model will include: Fixed Categorical: TRT, EP and their interaction term (TRT*EP). Interaction will

Key Secondary Efficacy Statistical Analysis	
Fixed Continuous Covariates:	be included only if the interaction is statistically significant (at 0.1 level of significance). GA and interaction term (TRT*GA). Interaction will be included only if the interaction is statistically significant (at 0.1 level of significance).
Repeated:	None
SAS Code	

 Analysis of Covariance: <pre>ods output lsmeans=means diff=diffs tests3=tests; proc mixed data=xxx; class EP TRT; model log_LoS= TRT EP GA TRT*EP TRT*GA/ddfm=kr s; lsmeans TRT /pdiff cl alpha=0.05; run;</pre> Wilcoxon rand sum test: <pre>proc npar1way data=xxx Wilcoxon; class TRT; var log_LoS; ods output wilcoxontest=wtest; run;</pre> 	
Model Checking & Diagnostics	

 Refer to Appendix 9: Model Checking and Diagnostics for Statistical Analyses. 	
Model Results Presentation	

 For binary endpoints, the number and percentage of subjects in each treatment group, the relative risk (RR) and 95% CIs, the odds ratio (OR) of response rates (retosiban versus atosiban) and 95% CIs, and p-value will be presented. The model-adjusted length of stay will be presented for each treatment group. In addition, the treatment difference between retosiban and atosiban and associated 95% CIs and p-values will be presented. Observed values using descriptive statistics for length of stay will be presented for each treatment group. For proportion of neonates with any of the composite component, neonates with any of the composite component w/o RDS, neonates with any of the composite component w/o RDS and mortality, and individual composite component, RR and 95% CIs, OR and 95% CIs, and p-values will be provided. 	
Sensitivity and Support Statistical Analysis	

 For length of stay, data will be analyzed in a similar fashion as described in Section 7.1.2. 	

Key Secondary Efficacy Statistical Analysis

- Treatment effects within defined subgroups in Section 5.1 will be explored.

8.1.3. Planned Other Secondary Efficacy Statistical Analyses

Other Secondary Efficacy Statistical Analysis
Endpoint

 • Proportion of neonates with any of the composite neonatal morbidity and mortality excluding RDS • Proportion of neonates with each individual component of the composite neonatal morbidity and mortality endpoints listed in Section 11.5.4. • Neonatal admission to a specialized care unit and length of stay – confirm admission to neonatal intensive or specialized care unit from the medical records • Newborn hospital readmission and length of stay – confirm any neonatal hospital readmission following the birth hospitalization, the reason for admission, and the length of stay from the medical records • Ambulatory surgery – confirm any neonatal ambulatory surgery and the indication for surgery from the medical records • Proportion of births prior to 28^{0/7} weeks' gestation • Proportion of births prior to 32^{0/7} weeks' gestation • Proportion of births prior to 35^{0/7} weeks' gestation • Proportion of births ≤7 days from the first study treatment • Proportion of births ≤48 hours from the first study treatment • Proportion of births ≤24 hours from the first study treatment
Model Specification

 • Binary endpoints will be analyzed in a similar fashion to the neonatal composite analysis in Section 8.1.2. • Neonatal admission to a specialized care unit and length of stay, and ambulatory surgery will be explored in the integrated analysis separately.
Model Results Presentation

 • Data will be analyzed in a similar fashion as described in Section 8.1.2. • Treatment effects within defined subgroups in Section 5.1 will be explored.

